6.0 Recruitment Methods

LOCAL:

- 6.1 This study will start with the retrospective phase which does not involve recruitment of patients, but involves analysis of existing data. De-identified data will be obtained from Cigna-Healthspring.
- 6.2 The project will be implemented in collaboration with Cigna-Health Spring, a Medicare Advantage Plan in Texas. The health plan has several electronic data files available for analysis including membership file, member

A motivational interviewing intervention customized by patient adherence patterns (NCT03985098) – 03.28.2018

summary file, institutional claims file, professional claims file, quest lab, Cigna-Health Spring's medical claims file (CCMS) and pharmacy file. Pharmacy files contain Part D pharmacy data provided by pharmacy benefits manager including patient/ drug identifying information, fill dates, days of supply, quantity dispensed and dosing for each prescription filled. The refill data will be used to determine the non-adherent patients. ICD-10 codes will be used to determine other exclusions using professional claims data.

Phase 2 will involve project intervention which will be conducted over the phone. A list of actively enrolled members, taking the medication who were a part of phase 1 will be created by Cigna HealthSpring to be used for intervention implementation at their premises. The phone call will be made by University of Houston pharmacy students who will be on rotation at Cigna-HealthSpring. The form of informed consent which will be read to the patient is attached to the IRB. If the patient consents to receive the intervention over the phone, and completes the phone call, the patient forms a part of the intervention group. Five follow-up phones will be attempted one month apart for the patient after the initial call.

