9.3 Phase 2: intervention implementation

Patients that are still enrolled in the health plan during 2017-2018 will be included in phase 2. Patients will be categorized by their adherence trajectory identified in phase 1 and will be randomized to intervention vs. not within each category. The proposed intervention will be a telephone call by a pharmacy student participating in rotations at Cigna-Health Spring Plan and trained in MI and 6 monthly follow up calls. During implementation, students will first examine the patient adherence pattern that was identified in phase 1 which will be coded. The student will then confirm the diagnosis, medication name, and dose with the patient answering the call and will follow the outlined protocol. Using MI, students will assess readiness for change, help patients identify potential barriers in accordance with patient past pattern of use, and guide them to develop a plan to deal with these barriers

A motivational interviewing intervention customized by patient adherence patterns (NCT03985098) – 03.28.2018

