Additionally, the students will ask the 2 questions from the Patient Health Questionnaire (PHQ)-2, a validated screening tool for depression (attached). If the patient responds positively to either question, the student will suggest that the patient schedules an appointment with his/her healthcare provider to discuss these symptoms. The Supervising pharmacists will be available to assist the students in answering any medication related questions that may arise during the calls and arrange for a diabetes educator to contact the patient at a later time if needed. Follow up phone calls will be performed each month for a total of six calls. Students will be supervised by the pharmacist preceptors and managed care pharmacy residents throughout the calls and intervention implementation. The students who will be implementing the calls will attend a three day MI training facilitated by [name], who is experienced in utilizing motivational interviewing to improve adherence. The students will practice calls as a part of their training. They will also complete Human Subjects Research training before their rotation at Cigna Healthspring, and the certificates will be uploaded to the IRB application. After each initial call, students will record the date and write a summary of the interaction with the patient documenting the main barrier/s identified in the conversation and the plan made with the patient. During the follow up calls, students will emphasize the information, confirm problem solved, provide further encouragement and reinforce adherence.

Control group: For every patient that received a call, a control will be randomly selected from the list of patients randomly assigned to the control group.

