20.0 Data Management

- 20.1 The data which will be provided by Cigna will contain data with encrypted patient IDs. The electronic data files for this study will be processed on a dedicated, layered-security server, which can be accessed only by [name] and designated project staff members who are under the direct supervision of [name]. Since the system is behind multiple firewalls, is monitored regularly, and is accessible only to key personnel, the risk of unlawful penetration is not a significant data safeguard concern. Data will be stored on the secure server for 3 years following the completion of the study. All analysis will be conducted on the desktop at UH College of Pharmacy. The data will not be accessible through any personal computers.

SAS 9.4 is the statistical software, which will be used for the analysis.

A motivational interviewing intervention customized by patient adherence patterns (NCT03985098) – 03.28.2018

Baseline characteristics: Comparisons in baseline characteristics will be made between the 2 study groups (intervention vs. control) using t-tests for continuous variables and chi-square tests for categorical variables. The characteristics evaluated will include predisposing factors: demographics, and number of other medications used; enabling factors: health plan (LIS vs. not), prescriber specialty (specialist vs. primary care); need factors: comorbidities (CHF, MI, CAD, stroke, ESRD, depression), previous hospitalization and CMS risk score.

Baseline PDC in the 12 months prior to intervention and patient past adherence trajectory will also be compared between 2 groups. Because of the randomization, we do not anticipate any significant differences between the two study groups on these characteristics.

Outcome analysis: Refill data during 2 time periods -- 6, and 12 months, following the initial call of the intervention will be evaluated to calculate adherence rates for both the intervention and control groups. The two periods were chosen to evaluate the intervention effect during the 6 months when the follow up calls were ongoing as well as after these calls had stopped. The adherence rate will be defined as proportion of days covered (PDC) for six and twelve month follow up period following the intervention. An intent to treat analysis will be utilized.

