To examine the effect of study group (intervention vs. control) on adherence, study group PDC means for each follow up time, 6 and 12 months, post intervention will be calculated and compared using a t-test. In the event that significant differences in baseline characteristics were observed, multiple regression will be utilized to adjust for the imbalance. The outcome variable will be PDC during each follow up period, 6 and 12 months, following the intervention initial call. The primary exposure variable will be study group, and other covariates will include any baseline characteristics not equally distributed.

Dichotomization of the outcome: Patients in both groups will also be categorized as adherent vs. not during the two follow up periods based on PDC \geq 80% in each time period, 6 and 12 months, to create 2 categorical outcome variables. The effect of study group on adherence will be evaluated for these categorical outcomes using chi-square tests. If significant differences in baseline characteristics were observed, logistic regression models will be utilized to adjust for imbalances

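### The intervention group is formed from patients who consent to and complete the first call, after randomisation, while the intent-to-treat set is left undefined

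*Combined protocol and SAP*

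**What the plan says.** Section 9.3 categorises patients by phase 1 trajectory and says they "will be randomized to intervention vs. not within each category". Consent comes later: under section 17.0 the student reads the consent letter on the phone and the patient may refuse. Section 6.2 then says that if the patient "consents to receive the intervention over the phone, and completes the phone call, the patient forms a part of the intervention group".

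For the comparison group, section 9.3 says: "For every patient that received a call, a control will be randomly selected from the list of patients randomly assigned to the control group". No contact, consent or completion condition is placed on controls, and the draw is not said to be within trajectory. Section 5.2 counts 250–300 intervention patients and, with one control each, 500–600 in total.

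On analysis, section 20.0 says "An intent to treat analysis will be utilized" and does not define the set. It expects baseline balance: "Because of the randomization, we do not anticipate any significant differences between the two study groups on these characteristics". If balance fails, "In the event that significant differences in baseline characteristics were observed, multiple regression will be utilized to adjust for the imbalance". Refill data in the 6 and 12 months "following the initial call of the intervention will be evaluated to calculate adherence rates for both the intervention and control groups".

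Non-completion is foreseen: section 15.0 has students log contact attempts as well as successful calls.

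**The concern.** Randomisation makes the two allocated lists comparable. Section 6.2 then describes an intervention group that has passed two further filters, agreeing to the call and finishing it, which the controls have not passed. People who can be reached and will complete a call about adherence may refill differently with no intervention at all. If they refill better, the difference would be read as benefit; if worse, it would hide benefit.

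The point reaches the main comparison, the t-test on mean PDC. It also reaches the start of follow-up: a patient who is never reached has no initial call, and no equivalent date is defined for controls. An analysis of everyone as allocated therefore cannot be run from the text as it stands.

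**Working it through.** **1. The plan's own figure.** 2 × 250 = 500 and 2 × 300 = 600, so section 5.2's total reproduces. It fits groups built from completed calls plus one control each, but the section does not say whether the 250–300 are randomised, released for calling or completed. If they are completers, the numbers allocated to intervention would be 250/c to 300/c for completion share c: 358–429 at 70%, 500–600 at 50%, 834–1,000 at 30% (rounded up).

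**2. The bias formula.** Let m1 and m0 be the mean untreated PDC of completers and non-completers. By randomisation the control list has expected mean c·m1 + (1 − c)·m0, and a random draw from it keeps that mean. With no true effect, completers minus controls is

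m1 − c·m1 − (1 − c)·m0 = (1 − c)(m1 − m0) = (1 − c) × gap.

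The control draw adds no bias. All of it comes from the selection in the intervention arm.

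**3. Illustration.** The documents give no completion share, gap, SD or significance level. Assumed: SD of PDC 0.25–0.35 and a two-sided 5% test; n = 250 or 300 per group as in section 5.2. With b = (1 − c) × gap and SE = SD × √(2/n), the rejection rate is 1 − Φ(1.96 − b/SE) + Φ(−1.96 − b/SE). The SE runs from 0.25 × √(2/300) = 0.0204 to 0.35 × √(2/250) = 0.0313.

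| Completion | Gap | b | Unadjusted rejection, no true effect |
|---|---|---|---|
| any | 0 | 0 | 5% |
| 70% | 0.05 | 0.015 | 8–11% |
| 50% | −0.05 | −0.025 | 13–23%, almost all against the intervention |
| 50% | 0.10 | 0.05 | 36–69% |

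**4. Does the conditional adjustment repair it?** Take the last row and assume the baseline PDC gap is also 0.10. Adjust for baseline PDC only when it differs significantly. The trigger then fires in only 36–69% of trials, and the overall rejection rate is 21–35% if baseline and follow-up PDC correlate at 0.5, or 13–18% at 0.8. This models one covariate; section 20.0 could adjust for several. No measured covariate fully captures willingness or reachability.

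**5. Cost of analysing as allocated.** Assume SD 0.30 and an effect in completers that gives 80% power at 250 per group: d = (1.96 + 0.842) × 0.30 × √(2/250) = 0.075. With the same 250 completed calls, each arm has 250/c patients and the expected difference is c × d.

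| Completion | Per arm | Power, unadjusted | Power, adjusted for baseline PDC (correlation 0.5, residual SD 0.30 × √0.75 = 0.26) |
|---|---|---|---|
| 70% | 357 | 65% | 77% |
| 50% | 500 | 51% | 63% |
| 30% | 833 | 34% | 43% |

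**The case against.** A reader might infer a flat contradiction between sections 6.2 and 20.0. The text does not go that far. Section 6.2 says that completers form part of the intervention group, not that only completers do, and it sits under recruitment rather than analysis. Sections 7.2 and 13.0 let patients decline later calls, so intent to treat may have been meant as keeping everyone who completed the first call, whatever they did afterwards. On that reading the sections agree. But the comparison is then still not the randomised one, so the defence removes the contradiction and leaves the problem.

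A reader might also blame the control draw in section 9.3. That draw is random from the allocated controls and excludes no intervention patient, so it is not a source of bias. Its wording (received a call) may also cover more patients than section 6.2's (completed the call), so even the number of controls is not fixed.

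Third, controls could take the call date of the patient for whom they were drawn. That is possible, but it is not stated and gives no date to patients who are never reached.

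Fourth, the rejection rates rest on inputs from outside the documents, and mild inputs give mild inflation. This stands: the figures show a range and do not predict this trial.

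**Conclusion.** The point holds as a defect in how the compared groups are defined. Section 20.0 names intent to treat without saying whether allocated patients who were not reached, refused or stopped the first call are analysed. Section 6.2, supported by the counts in section 5.2, points to leaving them out. If section 6.2 is followed, the expected balance credited to randomisation does not apply to the groups compared, and adjustment that depends on a significant baseline difference cannot restore it.

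Size and direction are unknown. The illustrative range runs from no inflation at zero gap to 36–69% false rejection at 50% completion and a gap of 0.10, on assumed completion, gap and SD. It would be tempting to conclude that patients will be excluded, or that benefit will be overstated; the documents establish neither. The case for change rests on the undefined set and its tension with section 6.2, not on any one figure. It is more than a missing detail, because the two readings compare different patients in the main analysis.

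**What to change.** Revise sections 6.2, 9.3 and 20.0 as follows.

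- Define the primary intent-to-treat intervention set as all patients randomised to intervention whose names are released for a call attempt, whether or not they are reached, consent or complete the call. If calling capacity is limited, release names in random order within trajectory.
- Compare them with all randomised controls, or with a control sample drawn within trajectory independently of call completion.
- Give both arms the same start rule, for example the list-release date with a matched date for controls in the same trajectory. A date close to the first attempt suits the stated aim: "The two periods were chosen to evaluate the intervention effect during the 6 months when the follow up calls were ongoing".
- Analyse by the trajectory strata used for randomisation. Report completers only as a secondary result.
- State whether section 3.1's exclusion of patients who disenroll or die applies to phase 2. If it does, it is a further post-allocation exclusion and must be reconciled with intent to treat.
- Restate section 5.2 as numbers randomised or released per arm, as well as calls completed.

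Outcomes come from refill claims, so non-completers can be followed without contact, and attempts and successful calls are already logged. The work is wording, a larger extract, and fields for assignment, release date and call completion.

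Two downsides should be stated. First, the effect is diluted, as the power table shows. Restoring 80% power at 1:1 without adjustment needs 250/c² per arm: 511, 1,000 or 2,778 at 70%, 50% or 30% completion. That implies about 358, 500 or 833 completed calls, against the 250–300 intervention patients in section 5.2. Baseline adjustment and extra claims-only controls recover part of the loss: at 50% completion, 500 versus 2,000 gives about 71% unadjusted or 82% adjusted, if enough non-adherent patients exist (the documents give no number). Second, the ethics board should confirm that de-identified claims of patients who refuse the call may be used; controls are already analysed without a call.

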7.0 Study Timelines

- 7.1 The duration of the total study will be 3 years. Retrospective analysis of phase 1 and intervention development will require 12 months. The retrospective analysis will use data from July2016-January 2018. July – December 2016 will be used for baseline covariate measurement. January 2017- January 2018 will include adherence measurement. However this is de-identified patient data used for retrospective analysis and does not require patient participation.
- 7.2 The phase 2 of the study will involve the intervention call provided in the day of consent followed by monthly follow-up calls for six months. The patient however can refuse to participate in any of the calls, even if the patient has completed the primary phone call
- 7.3 The number, frequency and length of study visits: One intervention call lasting 12-15 minutes on average. Monthly follow up calls to the patients who received the initial call for six months lasting on an average for 5-10 minutes.(First call + 5 follow-up calls)
- 7.4 The duration anticipated to enroll all study subjects: The enrollment will continue for a period of 8 months (equivalent to an 2 active semesters)
- 7.5 The estimated date for the investigators to complete this study: 3 years Timeline details below

**A motivational interviewing intervention customized by patient adherence patterns
(NCT03985098) – 03.28.2018**

	Pre-award	Study Period: 36 months																	
		1 2	3 4	5 6	7 8	9 10	11 12	13 14	15 16	17 18	19 20	21 22	23 24	25 26	27 28	29 30	31 32	33 34	35 36
IRB Approval																			
Phase 1 trajectory modeling																			
Intervention Development																			
MI training and randomization																			
Intervention implementation																			
Post intervention analysis																			
Manuscript / Final report prep																			

8.0 Study Endpoints

- 8.1 Develop group-based trajectory models to identify patients with similar medication filling behavior patterns among patients utilizing ACEI/ARBs with co-morbid HTN and DM enrolled in a MAP and examine predictors associated with having different trajectories.
- 8.2 Customize a pharmacy student telephone intervention incorporating MI by patient adherence behavior patterns identified under aim 1.
- 8.3 Demonstrate the benefit of the customized intervention on ACEI/ARB adherence among non-adherent patients with co-morbid HTN and DM enrolled in a MAP.

9.0 Procedures Involved

9.1 Phase 1: Retrospective data analysis

Patients that used a study medication during January 2017 will be identified and the first prescription date during this time will be considered the index date. A dummy variable will be created to indicate prevalent user vs incident user by evaluating the 6 month data prior to index date (July – December 2016). Patient adherence will be assessed during the one year following the index date.

Adherence will be measured as proportion of days covered (PDC). PDC rates over the entire 360-day assessment period will be determined. PDC will also be calculated separately for each month during the one year following the index date. During each of the 12 consecutive 30-day periods of adherence assessment, a binary indicator for “full adherence” each month, defined as PDC= 0.8 vs. non-adherence will be created. The 12 binary indicators of full adherence will then be modeled during each 30-day period as a longitudinal response in a logistic group-based trajectory model. Patients will be assigned to a trajectory on the basis of these models. Several logistic regression models will then be carried out to identify predictors associated with specific trajectories for adherence.

9.2 Covariates: Demographics (age, gender, and language), physician specialty (primary care vs. specialist), health plan (low income subsidy vs.

A motivational interviewing intervention customized by patient adherence patterns (NCT03985098) – 03.28.2018

other), prevalent vs. incident user, Centers for Medicare and Medicaid CMS Risk Score, Charlson comorbidity index (CCI) and number of distinct medications. Additionally, selected co morbidities will be identified by ICD-10 codes during the one year prior to index date including congestive heart failure, coronary artery disease, peripheral vascular disease, myocardial infarction, diabetes, stroke hypertension, end stage renal disease (ESRD), chronic obstructive pulmonary disease, asthma, and depression. To ensure appropriate risk adjustment in the models, additional covariates which will be added to the model include, regimen complexity, class of antihypertension medication used, baseline adherence measured as PDC, previous hospitalization and patient's trajectory prior to intervention.

Customization of intervention: After completion of the retrospective analysis phase and identifying the major trajectories in this patient population, the team will meet to discuss the patterns identified, the potential barriers likely to be associated with each trajectory, and strategies that can help patients within each trajectory based on their behavior pattern. The team will then develop customized education specific to each identified trajectory. For example: some patients can have high medication use in the early part of the follow up period but poor after, others may have low initial use and improved subsequent. Some may have intermittent adherence throughout the follow up time, others may simply discontinue. The expected barrier and potential solutions that should be discussed with the patient using MI strategies will vary accordingly. Patients past adherence patterns will guide the team in determining probable barriers and what can potentially help the patient. For example, patients who discontinue the medication may have side effects concerns or may view the medication as unnecessary. Patients who continue to take medication but have less than 0.8 PDC throughout may be forgetting to take the medicine and need help remembering. The team will create a code for each trajectory identified to categorize the patients. A protocol for each trajectory will be developed to summarize the education that is likely to benefit patients with the specific behavior pattern given the code. All the developed protocols will be based on the Ask-Provide-Ask approach, a pharmacist adaptation for the Elicit-Provide-Elicit approach of MI (attached)

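### PDC makes no allowance for hospital or skilled-nursing days, so a refill delayed by a stay can be scored as non-adherence (cheap improvement)

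*Combined protocol and SAP*

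**What the plan says.** Section 6.2 names the source of fills: "Pharmacy files contain Part D pharmacy data provided by pharmacy benefits manager". It adds that "The refill data will be used to determine the non-adherent patients".

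Section 9.1 sets the measure and the windows. "Adherence will be measured as proportion of days covered (PDC", and "PDC rates over the entire 360-day assessment period will be determined". PDC is also taken over twelve 30-day periods, each cut at 0.8. The twelve indicators feed the trajectory model, and logistic regressions then look for predictors of trajectory (objective 8.1).

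Section 20.0 carries the measure into Phase 2: "The adherence rate will be defined as proportion of days covered (PDC) for six and twelve month follow up period".

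No section says how days in a hospital or skilled nursing facility enter the numerator or denominator, or whether home supply left unused during a stay is carried forward. Yet section 6.2 lists among the available files "institutional claims file, professional claims file, quest lab", and the first of these could date the stays.

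The covariates in section 9.2 include heart failure, infarction, stroke, ESRD, the CMS risk score and the Charlson index. A further list for risk adjustment has "baseline adherence measured as PDC, previous hospitalization". The hospitalisation covariate refers to earlier stays, and nothing listed measures stays during the 360 days.

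**The concern.** A patient admitted to a facility normally receives the drug there, and no outpatient fill is recorded. The home supply then lasts longer. A patient who uses it up before refilling shows a gap in the Part D file without having missed a dose.

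The error can only lower PDC, and it falls on patients who have stays. The candidate predictors in section 9.2 are largely conditions that make stays more likely. Adjusting for baseline severity does not remove the error, because it sits in the outcome and loads on those same predictors. The exclusion of patients who die or disenrol (section 3.1) leaves in survivors who had stays.

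At stake are the predictor results under objective 8.1 and, for patients with long or repeated stays, the trajectory label. Under section 9.3 that label sets both the randomisation stratum and the call protocol.

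**Working it through.** The plan states no figure on this point, so there is none to reproduce.

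**1. Thresholds, from the plan's own windows and cut.** Section 9.1 is read as PDC of at least 0.8, as section 20.0 writes it.
- 30 days: 6 uncovered gives 24/30 = 0.80, adherent; 7 gives 23/30 = 0.767, not adherent.
- 180 days: 36 uncovered days are tolerated; 37 cross the cut.
- 360 days: 72 are tolerated; 73 cross. A patient otherwise at PDC 0.85 (306 days covered) crosses after losing 19: 287/360 = 0.797.

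**2. Range of loss for a stay of L days.** Between 0 and L/window.
- 6-month PDC, L = 25: 0 to 25/180 = 13.9 points.
- 360-day PDC, L = 7: 0 to 7/360 = 0.019. L = 30: 0 to 30/360 = 0.083.

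**3. A gap placed at random against the 30-day grid.** A 7-day gap flips a month only when all 7 days fall in one window: 24 of 30 start positions, or 80%. A 10-day gap does so in 27 of 30 (90%). A gap of 13 or more days always does, since one of the two windows holds at least 7 days.

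**4. One stay in a fully adherent patient.** Assumed, as the documents give none of it: stay length, 30- or 90-day fills starting on the index date, and three refill patterns. Share of admission days for which a monthly indicator flips (30-day / 90-day fills):

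| Stay | Leftover supply used first | Refill on schedule, or at discharge if supply ran out in the stay | Automatic refill |
|---|---|---|---|
| 5 days | 0% / 0% | 0% / 0% | 0% |
| 7 days | 93% / 76% | 0% / 0% | 0% |
| 20 days | 97% / 79% | 42% / 12% | 0% |
| 30 days | 100% / 82% | 77% / 21% | 0% |

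In the first pattern the gap starts on a window boundary because the fills are aligned with the grid, so the 30-day-fill figure exceeds the 80% in step 3. Mean 360-day PDC in that pattern is 0.982 / 0.985 for 7 days and 0.917 / 0.932 for 30 days. Only 0 to 9% of the days of a 7-day stay are themselves uncovered (0 to 48% for 30 days); most of the loss in the first pattern is the later refill gap.

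**5. Effect on a predictor's odds ratio.** Simulation with 60,000 patients per group and identical adherence at home. Assumed: half on 30-day and half on 90-day fills, mean hospital stay 6 days, 20 to 30% of stays followed by a mean of 25 facility days, refill delayed by the stay. Yearly stay rates without and with the predictor were 12% v 35%, 15% v 40% and 15% v 50%. The outcome is 360-day PDC below 0.8; the true odds ratio is 1.
- All patients delay: 1.06, 1.09, 1.13. A separately coded run gave 1.06, 1.08, 1.12.
- At least three non-adherent months as the outcome instead: 1.06, 1.07, 1.12.
- Half of patients delay: about 1.06.
- Nobody delays: 1.00 to 1.04, within simulation error of 1.
- Facility days removed and supply shifted: 0.99.

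**6. Trajectory label, illustration only.** Assume an adherent class with monthly probability 0.95, an intermittent class with 0.60, and equal priors. The likelihood ratio for k flipped months is (0.95^(12−k) × 0.05^k) / (0.60^(12−k) × 0.40^k).
- k = 1: 0.02844/0.001451 = 19.6, so the posterior for the adherent class is 19.6/20.6 = 95%.
- k = 2: 0.001497/0.000967 = 1.55, posterior 61%.
- k = 3: 0.0000788/0.000645 = 0.122, posterior 11%.

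**The case against.** The plan is silent; it does not state that facility days count as uncovered, and an adjustment could sit in a PDC algorithm that is not described. That is possible, but a plan should state such a rule, and the current wording points to all calendar days.

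A reader might infer that facility days as such count as non-adherence. They do not: a day is covered while dispensed supply lasts, wherever the patient is. The loss depends on how far the refill is delayed, and with automatic refills it is zero. This stands.

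A reader might also turn the simulated odds ratios into a false-positive rate of about 37 to 90% at n = 22,000. The documents do not support that. Stay rates and refill behaviour are not given. The 22,000 in section 5.1 is the expected dataset, while section 3.2 applies the criteria at analysis, so the final cohort may be smaller. The outcome simulated is 360-day PDC below 0.8, whereas section 9.1 regresses trajectory membership. Halving the bias alone would bring the rates to about 13 to 38%.

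It is also tempting to say that the plan tests hospitalisation as a predictor of trajectory. Section 9.2 places it among the additional adjustment covariates, next to the trajectory before intervention, so that list may belong to the Phase 2 model.

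Harm from a wrong call protocol is not shown for one short stay, as step 6 illustrates. Finally, objective 8.1 concerns filling behaviour, and a late fill is part of that. But section 9.1 labels the result adherence, and section 9.2 (customization of intervention) reads patterns as forgetting or discontinuing.

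**Conclusion.** The point holds as a cheap improvement. PDC has no adjustment for facility stays, although a file that could supply one is listed. Any resulting error lowers PDC, by between nothing and the length of the stay, and 7 or more uncovered days in a window flip that month's indicator.

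Phase 1 predictor odds ratios can be modestly biased: about 1.00 to 1.13 for 360-day PDC below 0.8. This rests on assumed stay rates, stay lengths, fill sizes and refill delay, and on heart failure, infarction, stroke, ESRD and the CMS risk score predicting stays, which is plausible but not shown in the documents. The effect on trajectory membership was not computed. Longer or repeated stays could change a trajectory label; how often is unknown.

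A reader might infer that the Phase 2 treatment effect is biased. It is not, provided the arms are compared as randomised, as the intention-to-treat statement in section 20.0 implies: stays should then be similar in both arms. They add some noise to 6- and 12-month PDC and can push individual patients below 80%.

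**What to change.** In sections 9.1 and 20.0:
- Take inpatient and skilled-nursing days from the institutional claims file and remove them from both numerator and denominator of PDC.
- Move home supply that overlaps a stay so that it starts the day after discharge.
- Apply the rule identically to the 30-day, 360-day, baseline, 6-month and 12-month PDC, and in both arms.
- Set a 30-day window spent wholly in a facility to missing in the trajectory model.
- Report the unadjusted PDC as a sensitivity analysis, so that the size of the adjustment can be seen.

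The cost is protocol wording and some SAS programming on a file the plan already lists; the Phase 2 data request should include the same file. The drawback is slight over-crediting of patients who refill on schedule during a stay.
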